SPECIFIC AIMS. In the last decade, VA has made significant strides in suicide prevention, particularly for Veterans receiving Veterans Health Administration (VHA) care. However, most of these efforts have focused on downstream interventions to reduce suicidal behavior among those already identified to be at high risk (e.g., High-Risk Flag, post-discharge treatment policies). In contrast, more upstream efforts, such as population-based screening for suicide risk, have not been systematically implemented across **VHA settings.** Instead, suicide risk screening and evaluation in VHA has traditionally been limited to select patient cohorts or treatment settings (e.g., those with a known psychiatric disorder). However, emerging evidence indicates that many individuals who die by suicide are not identified as having a psychiatric disorder and often present for nonbehavioral health care prior to their death²⁻⁴. Given that early and accurate detection of suicide risk among **all Veterans** presenting for VHA care is a critical component of VA's National Strategy for Preventing Veteran Suicide 2018-2028⁸, VHA leadership mandated implementation of a national suicide risk identification strategy, VA Risk ID, beginning October 1, 2018. The goal of VA Risk ID is to improve the detection and management of suicide risk by standardizing suicide risk screening and evaluation enterprisewide. VA Risk ID incorporates staged evidence-based/informed tools and processes. The three stages include two levels of screening, followed by a Comprehensive Suicide Risk Evaluation (CSRE). VA Risk ID moves beyond selective screening and evaluation (i.e., based on known risk factors) and expands these practices to a broader population of patients presenting to a wide variety of medical settings.

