Thus, the objective of this national quality improvement project is to develop an adaptive strategy to improve implementation of VA Risk ID to fidelity. Using a sequential multiple assignment randomized trial (SMART) design, two evidence-based implementation strategies will be evaluated: 1) Audit and Feedback (A/F); 2) A/F plus External Facilitation (A/F+EF). We will evaluate these strategies across several domains based on the RE-AIM OUEST mixed methods framework⁹. In addition to focusing on implementation outcomes, such as the impact of these strategies on implementation of VA Risk ID to fidelity, and potential barriers to adopting these strategies, we will also examine the impact of the clinical innovation (i.e., VA Risk ID) on patient-level outcomes. **Primary Aim:** Among sites that do not meet the benchmark for adequate performance (i.e., completion of secondary screening and CSRE for 80% or more of eligible patients) following 6 months of Implementation as Usual (IAU), does the addition of A/F for 10 months significantly improve scores on VA Risk ID performance measures compared to IAU alone? Secondary Aims: 1) Among sites that continue to not meet the benchmark for adequate implementation after 10 months of A/F, does the addition of EF significantly improve scores on VA Risk ID performance measures compared to A/F alone? 2) Among sites that meet the benchmark following A/F alone, is performance maintained following discontinuation of A/F? Outcomes for primary and secondary aims will use clinical performance measures extracted from VA's External Peer Review Program (EPRP) that reflect key practice elements of VA Risk ID: completion of the primary suicide screen, timely completion of the secondary suicide screen and timely completion of the CSRE. Exploratory Aims: 1) Examine the extent to which VA Risk ID is reaching the intended population and compare the characteristics of Veterans reached to all Veterans eligible for screening: 2) Examine contextual factors that may impact the a) implementation of VA Risk ID to fidelity and b) adoption of the implementation interventions. 3) Examine whether Veterans who receive the CSRE are more likely to receive a safety plan than Veterans who screen positive on the primary screen only. **This project directly**

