Several implementation strategies have been employed to support national implementation of VA Risk ID. To date, a multi-faceted approach has been used to support implementation of the three-stage screening and evaluation process. Strategies have included critical information technology enhancements (i.e., new informatics tools and clinical reminder updates), educational webinars, facility champions, weekly technical assistance calls focused on troubleshooting and building a community of practice, support email address, and a fallout report dashboard to help facilities track incomplete secondary screens and CSREs. Despite these efforts, some facilities will face challenges to implementation. *To*

facilitate continuous quality improvement (QI) of VA Risk ID, ongoing evaluation of VA Risk ID and interventions to improve implementation are needed.

Performance measurement is a critical component of evaluation and ongoing QI. A critical element of any QI program is the ability to reliably measure performance. The VA has been a pioneer when it comes to measuring performance as an essential mechanism in improving quality of care¹¹. The External Peer Review Program (EPRP¹²) is the official data source for monitoring facility performance, which is used to prioritize the quality areas needing most attention. Moreover, there is evidence to suggest that facility performance measurement significantly improves overall quality of care across various conditions¹³⁻¹⁴. In preparing for VA Risk ID implementation, several clinical performance measures that map onto the 3-stage screening and evaluation process for those eligible for depression and PTSD screening were developed. These measures provide a standardized way of monitoring implementation of VA Risk ID to fidelity across VHA facilities and include: **sui40** and **sui51**- completion of primary suicide screen as part of depression and PTSD screening, respectively; **sui2**- same day completion of the secondary screen following a positive primary screen; and **csra1**- same day completion of the CSRE following a positive secondary screen.

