C1. Evaluation Framework. RE-AIM QUEST⁹ will provide an overarching framework for testing the impact of the proposed adaptive implementation strategy. RE-AIM QUEST expands RE-AIM by allowing investigators to understand not only whether Reach, Effectiveness, Adoption, Implementation and

Maintenance vary across sites and conditions, but also how and why these variations occur⁹. Moreover, RE-AIM was selected because of its ability to provide an approach to evaluation that focuses both on the impact of the implementation interventions and the impact of the clinical innovation (Table 1).

RE-AIM Domain	Operationalization	Data Sources			
Level of Evaluation: Clinical Innovation					
Reach	The absolute number and representativeness of Veterans that received the primary, secondary screens and CSRE.	Administrative (CDW) Data			
Effectiveness	Whether Veterans who receive the CSRE are more likely to receive a safety plan (SP) compared to Veterans who screen positive on the primary screen only.	Administrative (CDW) data			
Implementation	Percentage of eligible Veterans sampled at each facility who receive the different stages of VA Risk ID as intended; barriers & facilitators to implementation to fidelity.	EPRP measures			
Level of Evaluation	on: Implementation Strategy				
Effectiveness	Effect of A/F intervention on implementation of VA Risk ID to fidelity compared to IAU alone. Effect of A/F + EF intervention on implementation of VA Risk ID to fidelity compared to A/F alone.	EPRP measures			
Adoption	Number of sites randomized to the implementation interventions that participated. Characteristics of participating/non-participating sites and reasons for participating/not participating.	Key Informant (KI) & Debriefing Interviews			
Implementation	mplementation Percent of sampled instances of implementation intervention delivered to fidelity (i.e., met criteria for adherence).				
Maintenance	Maintenance of adequate implementation following removal of A/F; Sustained implementation of VA Risk ID for high performers	EPRP measures			

Table 1. Application of RE-AIM, Level of Evaluation, Operationalization, and Data Sources

^a All domains will be evaluated at Baseline, Post-Intervention Phase I and II except for maintenance, which will be evaluated at postintervention phase I and II

C2. Design. a. Primary and secondary aims (Effectiveness and Maintenance of the implementation

Figure 2. SMART Design and Intervention Phases

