C3. Data Sources. a. VA Risk ID Clinical Performance Measures: Outcomes for primary and secondary aims will include four clinical performance measures extracted from VA's EPRP that reflect key practice elements of VA Risk ID: primary suicide screening (sui40 and sui51), secondary suicide screening (sui 2) and the CSRE (csra1). These four measures are currently in pilot status as they are being validated. EPRP measures are routinely abstracted monthly. VA Risk ID EPRP measures at baseline evaluation (month 6). month 10 of Intervention Phase I and month 10 of Intervention Phase II will be used to evaluate the effectiveness of the implementation strategies (primary and secondary aims). A specific advantage of using EPRP performance measures is that the actual abstraction and collection of data occurs independently from the evaluation team and program office. A data use agreement will be obtained to facilitate the use of EPRP data for this QI project. VA Risk ID EPRP Validation Process: VHA and EPRP contractors develop the data collection instruments (abstraction tools), which are programmed into abstraction software. Data are collected monthly by the abstractors for a random sample of Veterans and the contractor monitors for irregular abstraction patterns. Once final quarterly data are received, question level response patterns and scoring algorithms may be reviewed. Inter-rater reliability (IRR) on the measures will also be reviewed at least once a year. Upon the IRR review, additional edits may be made to the data collection instrument. Once the measure and instrument are considered stable and the data is considered reliable, they can move out of a pilot status. We anticipate that by the start of this project, these measures will be out of pilot status as they will have gone through several rounds of testing and revisions. If we encounter unanticipated and significant challenges to validation of EPRP VA Risk ID measures, we will use the RE-AIM domain of "reach" as our primary outcome measure. **b. Corporate Data Warehouse (CDW):** CDW is a database organized into a collection of data domains derived from the VHA electronic health record. It contains records of inpatient and outpatient care including dates and location of care, as well as associated ICD-10 codes. We will use electronically abstracted data to evaluate reach and effectiveness of the clinical innovation. For Exploratory Aim 1, specific sources of CDW data will include: 1) patient socio-demographic characteristics that allow for comparison between Veterans reached and all Veterans eligible for screening 2) patient responses and results from the screens for Depression, PTSD, and C-SSRS that are administered within Mental Health Assistant; 3) note templates containing the CSRE; and 4) Health Factors recording responses to the CSRE and date of CSRE administration. These sources of data will also serve as data sources for Exploratory Aim 3. Additionally, we will gather health factors specific to the suicide prevention safety plan details and dates. Free-text progress notes may also be abstracted if needed. c. IAU, A/F and EF Debriefing Interviews: Semi-structured interviews will be conducted by an independent evaluator monthly with study team members implementing IAU during the three project phases, A/F during Intervention Phases I and II and EF during Intervention Phase II. The purpose of the interviews is to gather information regarding implementation activities, program and implementation modifications, and implementation barriers and facilitators. The independent evaluator will also use this information to complete the A/F and EF Fidelity Checklists (see below). Draft interview guides are included in Appendix 3. d. Key Informant Interviews: Semi-structured interviews will be conducted with primary care (PC) and primary care mental health integration (PCMHI) leadership and providers after each of the three project phases via telephone. Interviews will explore barriers/facilitators to implementation as well as factors that impact the adoption and utility of the implementation interventions. All interviews will be conducted by the independent evaluator to reduce potential bias. Interviews will be audio recorded and recordings will be transcribed. Draft interview guides for each project phase are included in Appendix 3. e. IAU and EF Activity Logs: A/F and EF Adoption Logs: The IAU Activity Log contains the components of IAU and will be completed monthly throughout each study phase by the independent evaluator. The EF Activity Log²⁴ will be completed by facilitators weekly to track the facilitation activities completed for each site receiving facilitation. The A/F and EF Adoption Logs will be completed weekly by the study team member responsible for sending out A/F and EF communications. These data will be used to determine whether sites adopted the implementation interventions. See Appendix 4 for draft logs. f. A/F and EF Fidelity Checklists: Fidelity checklists will be used to ensure that A/F and EF were delivered as intended.

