EPRP outcomes of change in sui2 and csra1 from the 6th month of the baseline period to the 10th month of the first interventional phase will each be modeled as a function of group (A/F vs. IAU), the baseline outcome value, the stratification variables of facility complexity (high, medium, low) and baseline performance level (above or below the median average fallout rate), and geographic region (West, Midwest, Southwest, Southeast and Northeast). Inference will be made based on the coefficient associated with the group variable and 97.5% confidence intervals (CI) will be reported (alpha=0.025). A similar analysis will be used to determine the effect of A/F on the change in the EPRP outcome for the primary screeners (sui40 and sui51), with 95% CIs reported. **c.** Secondary Aims: 1). To test the effect of the addition of EF for those who do not implement adequately at end of interventional phase 1, the primary EPRP outcomes of change in sui2 and csra1 from the 10th month of interventional phase 1 (baseline for interventional phase 2) to the 10th month of interventional phase 2 will be modeled as a function of group, the baseline outcome value, the stratification variables and geographic region (if sample sizes allow for control of this variable). Inference will be made based on the coefficient associated with the group variable and 95% CIs will be reported. A similar analysis will be used to determine the effect of the addition of EF on the change in the EPRP outcome for the primary screeners (sui40, sui51), with 95% CIs reported. 2). An analysis similar to that described for secondary aim 1 will be employed to investigate the effect of discontinuing A/F for those who implemented adequately at the end of interventional phase 1. Lastly, we will use a data driven approach to characterize each of the four EPRP outcomes over time for each group outlined in Figure 2 (group 1-6). Mixed effects models with a random intercept and slope will be used to model each of the four EPRP outcomes as a function of categorical group (1-6) and an interaction between group and a Bspline transformation on time (allowing the outcome to vary smoothly over time, using 21-time points, i.e., the 6th baseline month and every month of each interventional phase) such that each group will have its own trajectory. The trajectory for each group will be plotted with pointwise confidence intervals. **d. Exploratory** Aims: *i. Reach*: Reach will be calculated using the following formula: actual number of Veterans screened or evaluated/ actual number of Veterans eligible for screening, calculated cumulatively across all three study phases and all sites. We will calculate reach for each assessment stage of VA Risk ID. We will examine representativeness of patients reached by comparing demographic characteristics and other relevant variables (e.g., settings in which screening was completed) between eligible Veterans who were screened and/or evaluated and those who were not. Given that Veterans are clustered within facility, if the intra-class correlation between Veterans within each facility is estimated to be greater than zero, methods appropriate for clustered data will be employed to compare the variables of interest. For continuous variables, linear mixed models will be used with a random facility effect and non-normal data will be transformed. For binary variables, generalized linear mixed models will be used with a logit link and for categorical variables, random effects multinomial models will be employed. If the ICC is zero, t-tests, Wilcoxon rank-sum, Chi-square or Fisher's exact tests will be used, as appropriate. *ii. Adoption & Implementation Factors:* Key informant interviews will be used to examine factors influencing adoption of the implementation interventions and barriers and facilitators of implementing VA Risk ID to fidelity. All qualitative data sources, including interview transcripts and documents will be compiled and managed using Nvivo V. 9.0 software. We will take a general inductive approach³⁴. Specifically, data analysis will be determined by both the research objectives (i.e., domains of the RE-AIM framework) and multiple readings and interpretation of the raw data (i.e., content analysis). The goal is to establish clear links between the research objectives and the summary findings derived from the raw data. *iii. Effectiveness- Clinical Innovation:* We wish to examine whether Veterans who receive the CSRE are more likely to receive a safety plan within 2 weeks than those who screen positive on the primary screen only. To account for clustering of Veterans within facility, a mixed-effects logistic regression will be used to model the outcome of safety plan within 2 weeks (yes/no) as a function of group (receipt of CSRE/positive on primary screen only) with a random subject within facility effect. Additionally, to determine if receipt of a timely safety plan depends on whether Veterans are considered to be at low, moderate or high acute risk of suicide, this model will be repeated with the addition of a group by (categorical) acute risk interaction. Odds ratios for receipt of CSRE relative to positive on primary screen only will be reported for each level of acute risk with 95% confidence intervals.

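### Exploratory Aim 3: the main safety-plan model compares groups already sorted by a suicide-risk screen, with no severity covariate, and the acute-risk model names no risk source for Veterans without a CSRE

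*Protocol*

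**What the plan says.** The Specific Aims state Exploratory Aim 3 as: "Examine whether Veterans who receive the CSRE are more likely to receive a safety plan than Veterans who screen positive on the primary screen only". Table 1 (C1) lists the same comparison under Effectiveness of the clinical innovation.

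Protocol C7 d.iii gives the analysis. A mixed-effects logistic regression will "model the outcome of safety plan within 2 weeks (yes/no) as a function of group (receipt of CSRE/positive on primary screen only", with a random subject-within-facility effect for clustering. No severity measure or other patient covariate is listed. Then "this model will be repeated with the addition of a group by (categorical) acute risk interaction", and "Odds ratios for receipt of CSRE relative to positive on primary screen only will be reported for each level of acute risk".

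On how a Veteran comes to have a CSRE, the Specific Aims describe "two levels of screening, followed by a Comprehensive Suicide Risk Evaluation (CSRE", and the csra1 measure in Section A is "same day completion of the CSRE following a positive secondary screen".

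Protocol C3 b lists the data for this aim: socio-demographics, "patient responses and results from the screens for Depression, PTSD, and C-SSRS", CSRE templates and health factors with dates, safety-plan health factors with dates, and free-text notes if needed. The SAP covers the Primary Aim and Secondary Aims 2a and 2b only, so it adds nothing on this aim.

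**The concern.** On the pathway described, CSRE recipients have screened positive twice. Veterans positive on the primary screen only either screened negative on the C-SSRS or were never given it. The groups are thus separated by a risk screen before the exposure occurs. If safety plans are written more often for Veterans at higher risk, the main odds ratio is above 1 even when the CSRE does nothing. Reported under Effectiveness, it could credit the CSRE with plans that follow from risk.

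The acute-risk model might reduce this, but each of its odds ratios needs that risk level to be known and populated in both groups. The plan does not say where the level comes from for Veterans without a CSRE.

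Two definitions are also open. One is whether the comparator includes missed secondary screens (or, less naturally, secondary-positive Veterans without a CSRE). The other is when the two weeks start. These are missing detail, but they decide how large the imbalance is.

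**Working it through.** The documents give no sample size, power or safety-plan rate for this aim, so there is no planned figure to reproduce. The check asks what odds ratio the main model gives when the CSRE has no effect.

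**Inputs from the documents (Protocol C5 a).** C-SSRS fallout f = 0.479 and CSRE fallout g = 0.612. Both are first quartiles across facilities; 75% of sites are higher. The 20% benchmark fallout is used as a second point.

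**Assumptions.**
- The truly secondary-positive share q among primary-positive Veterans is 0.25, 0.5 or 0.75.
- The safety-plan rates (a if positive, b if negative) are (0.5, 0.05), (0.3, 0.05), (0.3, 0.1), (0.5, 0.25) or (0.2, 0.1).
- All CSRE recipients are secondary-positive, and CSRE fallout means no CSRE.
- Missed screens have the same positive share as completed ones.
- Unidentified positives get plans at the same rate as identified ones.

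**Formulas.** L is the truly positive share of the comparator, r = La + (1 − L)b, and OR = [a/(1 − a)] / [r/(1 − r)].
- Reading 1 (secondary-negative plus missed): L = fq / [f + (1 − f)(1 − q)]
- Reading 2 (also secondary-positive without a CSRE): L = [fq + (1 − f)qg] / [f + (1 − f)(1 − q) + (1 − f)qg]
- Reading 3 (secondary-negative only): L = 0

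**Example.** Reading 1, q = 0.5, (0.5, 0.05): L = 0.2395/0.7395 = 0.324; r = 0.324 × 0.5 + 0.676 × 0.05 = 0.196; OR = 1/(0.196/0.804) = 4.1.

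**Ranges over the grid, no CSRE effect** (70%/80% is an assumed point above the first quartiles):

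| Comparator | 47.9%/61.2% | 70%/80% | 20%/20% |
|---|---|---|---|
| Reading 1 | 1.3 to 7.9 | 1.2 to 6.4 | 1.6 to 11.8 |
| Reading 2 | 1.2 to 5.9 | 1.2 to 5.4 | 1.4 to 9.2 |
| Reading 3 | 2.3 to 19 | 2.3 to 19 | 2.3 to 19 |

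With a = b the odds ratio is 1.0. Every value above 1 follows from assuming more plans at higher risk.

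**Acute-risk model.** Group (2 levels) by risk (3 levels) has 6 parameters. With all six cells filled, the design has rank 6 and all three odds ratios are estimable. With no high-risk comparator, the rank is 5. If risk is known only for CSRE recipients, the rank is 3 and none of the three is estimable.

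**Precision of a restricted comparison.** Per 1,000 primary-positive Veterans at 47.9%/61.2% and q = 0.5:
- recipients: 1000 × 0.521 × 0.5 × 0.388 = 101
- planned comparator (Reading 1): 1000 × (0.479 + 0.521 × 0.5) = 739
- secondary-positive without a CSRE: 1000 × 0.521 × 0.5 × 0.612 = 159

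The variance of the log odds ratio is the sum of 1/[np(1 − p)] over the two groups. For (0.5, 0.05) the standard-error ratio is √[(0.0396 + 0.0251)/(0.0396 + 0.0086)] = 1.16. Over the grid it is 1.11 to 1.23 at 47.9%/61.2% and 1.28 to 1.99 at 20%/20%. Clustering and covariate adjustment are ignored.

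**Dilution if exposure is same-day CSRE.** If a share s of CSREs is same-day (assumed 0.5 to 0.9), the part of the comparator that later receives a CSRE is (1 − g)(1 − s)/[(1 − g)(1 − s) + g]. At g = 0.612 this is 6% (s = 0.9) to 24% (s = 0.5). At g = 0.20 it is 29% to 67%.

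**The case against.** The aim is exploratory, worded as an association, and separate from the randomised comparisons. That stands and keeps the point minor, although the Effectiveness label still invites a causal reading.

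The magnitudes rest on assumed rates, and the first-quartile fallouts favour larger values: with missed screens in the comparator, most sites at that time would give smaller odds ratios. That also stands, with the qualification that C5 expects the share of sites below benchmark to fall. The figures show direction, not size.

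A reader might infer that the acute-risk odds ratios cannot be estimated. The documents do not support that. C3 b makes depression, PTSD and C-SSRS responses available for this aim and allows free-text notes, so a risk level for Veterans without a CSRE may be obtainable. No passage says risk comes only from the CSRE. What is missing is the rule that turns those sources into low, moderate or high.

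The restricted comparison is not clean either. Veterans who do not get the CSRE after a positive screen may differ from those who do, and a same-day definition puts later CSREs in the comparator. Both objections are right. The restriction removes the imbalance built in by the secondary screen and gives both groups one time origin, but it does not remove all confounding.

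**Conclusion.** The point holds as a minor one. The main model for Exploratory Aim 3 compares groups that differ in screened risk by design and carries no severity term. Its odds ratio therefore cannot separate a CSRE effect from severity if plans are more common at higher risk. The true size is unknown. Under the stated assumptions, at first-quartile fallouts, the no-effect odds ratio is about 1.2 to 8 with missed screens in the comparator and 2.3 to 19 for a secondary-negative comparator.

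The acute-risk part is conditional: the three odds ratios fail only if risk is known for CSRE recipients alone. A reader might also infer that the trial's effectiveness conclusions on A/F or EF are affected. They are not, because those aims use site-level performance measures and a different analysis.

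**What to change.** - Keep the stated contrast, so the aim and Table 1 stay as written. Define the comparator, state when the two weeks start, and label the odds ratio unadjusted and descriptive.
- Add a comparison restricted to Veterans with a positive secondary screen: CSRE versus no CSRE, adjusted for C-SSRS responses, with the two weeks counted from that screen in both groups and the clustering terms already planned.
- Handle CSRE timing explicitly. If exposure is same-day CSRE, so that it is known at time zero, state that later CSREs in the comparator dilute the contrast and add a sensitivity analysis that excludes or separates them. If any CSRE counts, state how CSREs and safety plans occurring during the two weeks are counted.
- Report safety-plan receipt by acute risk within CSRE recipients. Report group-by-risk odds ratios only where a comparable risk level, with its source stated, exists in both groups.
- Call the result an association.

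The cost is analysis text; the C-SSRS results, CSRE dates and safety-plan dates are already listed in C3 b. The comparator is smaller. For any CSRE versus none, the standard error of the log odds ratio rises about 11% to 23% at 47.9%/61.2% fallout and 28% to 99% at 20%/20%. For a same-day definition, with 50% to 90% of CSREs assumed same-day, it rises 13% to 52% and 5% to 78% respectively. Residual differences between Veterans who do and do not get the CSRE will remain.
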